5.2 Exclusion Criteria

Participants are excluded from the study if any of the following criteria apply:

- 1. Participant has a history or current evidence of a serious and/or unstable cardiovascular, respiratory, gastrointestinal, hematologic, autoimmune, blood dyscrasias or other medical disorder, including psychiatric disorders, cirrhosis, or malignancy. History of minor skin cancers (not including melanoma) or surgically treated, limited cervical carcinomas (ie, carcinoma in situ) are not exclusionary.
- 2. Participant is participating in another clinical study of any investigational drug, device, or intervention or has received any investigational medication during the last 30 days or 5 half-lives, whichever is longer, before baseline (Day −1).
- 3. Previous receipt of antibody or biologic therapy.
- 4. History of a previous hypersensitivity or severe allergic reaction with generalized urticaria, angioedema, or anaphylaxis to any of the ingredients of the VIS954 SC injection formulation.
- 5. Blood pressure > 160/100 mmHg or < 90/50 mmHg (may be repeated once if abnormal), at the screening visit or Day -1.
- 6. History of any infection requiring hospitalization or treatment with antivirals, antibiotics, or systemic antifungals within 3 months prior to screening.
- 7. Received a vaccination, other than COVID-19 vaccination, during the 30 days prior to administration of the first dose of study intervention. A COVID-19 vaccination cannot be received within 7 days prior to the first dose of study intervention and until 14 days after the last dose.

- 8. Has received any prescription or nonprescription (over-the-counter) medication during the last 30 days or 5 half-lives, whichever is longer, preceding baseline (Day -1), with the exception of acetaminophen, ibuprofen, naproxen (or other over-the-counter nonsteroidal anti-inflammatory drugs [NSAID]), hormonal contraceptives, topical medications, vitamins, and dietary or herbal remedies.
- 9. Any participant who has a recent history of alcohol or drug/chemical abuse, at the discretion of the investigator, will be excluded.
- 10. Enrolled participants must abstain from consumption of nicotine containing products from Day -1 through discharge.
- 11. Enrolled participants must abstain from consumption of cannabinoids from Day-1 through end of study.
- 12. For the duration of the study, enrolled male participants should not consume more than 15 standard drinks per week (7 days) and female participants should not consume more than 10 standard drinks per week (7 days). A standard drink equals 10 g of alcohol. Enrolled participants must abstain from consuming alcohol 48 hours prior to check-in on Day -1 through discharge.
- 13. Participant with a positive urine drug or alcohol breath screen test result at screening or Day -1. The urine drug screen and alcohol breath screen may be repeated once at the discretion of the investigator. The urine drug screen also screens for methylenedioxymethamphetamine and propoxyphene. If a participant tests positive on these tests, inclusion of that participant into the study will be based on the principal investigator's judgment with consultation, as needed, with the medical monitor and the sponsor.
- 14. Any chronic infectious disease (eg, chronic urinary tract infection, chronic sinusitis, bronchiectasis, active pulmonary or systemic tuberculosis [TB], chronic viral hepatitis such as hepatitis C or hepatitis B, or human immunodeficiency virus [HIV] infection).
- 15. Participant who has donated > 500 mL of blood within 60 days prior to start of the screening visit or the participant has donated any plasma within 7 days prior to baseline (Day −1).
- 16. Coronavirus disease 2019:
 - Current symptoms of infection.
 - Diagnosis of COVID-19 (reverse transcription polymerase chain reaction [RT-PCR], antigen testing, or clinical diagnosis) in the 21 days prior to screening.
 - Ongoing diagnosis of "Long-COVID" symptoms, due to a prior COVID-19 infection.

- 17. Is an employee of the clinical research team (any sponsor or research site employee), or has a family member who is an employee of these organizations.
- 18. Participant is judged by the investigator or the medical monitor to be inappropriate for the study.

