^dThe full physical examination will include, at a minimum, assessment of general appearance and an evaluation of skin, head, eyes (excluding fundoscopic examination of retinae), ears, nose and throat, chest and abdomen (excluding rectal examination), extremities, and musculoskeletal system. The brief physical examination will include, at a minimum, assessment of the general appearance, skin, cardiovascular system, respiratory system, and abdomen.

^eThe full physical examination on Day 1 will be performed at approximately 2 hours postdose (± 1 hour window).

^fVital signs will include blood pressure, pulse, body temperature, and respiratory rate. Height and weight will also be measured at screening. Vital signs measurements will be recorded on Day 1 within 30 minutes predose and at 2 and 4 hours postdose. At subsequent time points, vital signs will be recorded at approximately the same time of day, if possible and/or convenient.

gThe investigator or trained, qualified designee will assess the injection site for local tolerability at 1 and 4 hours postdose (Day 1), 24 hours postdose (Day 2), and on Days 3 and 29. Participants will also assess the pain associated with the injection using the Wong-Baker FACES Pain Rating Scale at the same time points.

^hSamples to be collected at 24 hours following the injection on Day 1.

iBlood samples for PK analysis will be collected on Day 1 (within 2 hours predose [± 1 hour], 4 hours postdose [± 1 hour], and 8 hours postdose [± 1 hour]), Day 2 (24 hours postdose [± 1 hour]), and Day 3 (48 hours postdose [± 1 hour]). All participants will also have blood samples collected for PK analysis on Days 5, 8, 11, 15, 22, 29, 36, 43, 57, and 71; there are no time points specified for the collection of PK blood samples on these days.

[figure not shown]
2 Introduction

VIS954 is a humanized immunoglobulin (Ig) G4 monoclonal antibody and orthosteric, insurmountable antagonist of human complement 5a receptor 1 (hC5aR1). C5aR1 is the receptor for the complement fragment and anaphylotoxin, C5a. C5aR1 is expressed on myeloid cells, including neutrophils. 1,2,3 The sponsor intends to develop VIS954 for the treatment of complement C5a mediated diseases

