7.1 Discontinuation of Study Intervention

Dose escalation will be stopped if the dose for a cohort is determined not to be safe or well tolerated. Specifically, the clinical study and dose escalation will be stopped if participants who received study intervention meet any of the following criteria:

- One SAE (unless the SAE is clearly not related to the study intervention, eg, a motor vehicle accident or clear alternative etiologies).
- Two participants experience a severe AE (Grade 3) or one participant experiences a potentially life-threatening AE (Grade 4) as per the standardized grading scale (Food and Drug Administration [FDA] Guidance for Industry: Toxicity Grading Scale for Healthy Adult and Adolescent Volunteers Enrolled in Preventative Vaccine Clinical Trials, Sep 2007). 12

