8.4.1 Time Period and Frequency for Collecting AE and SAE Information

All AEs and SAEs will be collected from the signing of the ICF until the last visit as specified in the Schedule of Assessments (Table 1.3-1).

Medical occurrences that begin before the start of study intervention but after obtaining informed consent will be recorded as Medical History / Current Medical Conditions, not as AEs.

All SAEs will be recorded and reported to the sponsor or designee immediately and under no circumstance should this exceed 24 hours, as indicated in Section 10.3. The investigator will submit any updated SAE data to the sponsor within 24 hours of it being available.

Investigators are not obligated to actively seek information on AEs or SAEs after conclusion of the study participation. However, if the investigator learns of any SAE, including a death, at any time after a participant has been discharged from the study, and he/she considers the event to be reasonably related to the study intervention or study participation, the investigator must promptly notify the sponsor.

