10.5 Appendix 5: Adverse Event Intensity Assessment

The standardized grading scales based on the FDA Guidance for Industry: Toxicity Grading Scale for Healthy Adult and Adolescent Volunteers Enrolled in Preventative Vaccine Clinical Trials, Sep 2007¹² are presented below.

Injection Site Assessment

Local Reaction to Injectable Product	Mild (Grade 1)	Moderate (Grade 2)	Severe (Grade 3)	Potentially Life-threatening (Grade 4)
Pain	Does not interfere to activity	Repeated use of non- narcotic pain reliever > 24 hours or interferes with activity	Any use of narcotic pain reliever or prevents daily activity	Emergency room visit or hospitalization
Tenderness	Mild discomfort to touch	Discomfort with movement	Significant discomfort at rest	Emergency room visit or hospitalization
Erythema/Redness ^a	2.5 - 5 cm	5.1 - 10 cm	> 10 cm	Necrosis or exfoliative dermatitis
Induration/Swelling ^b	2.5 - 5 cm and does not interfere with activity	5.1 - 10 cm or interferes with activity	> 10 cm or prevents daily activity	Necrosis

^aIn addition to grading the measured local reaction at the greatest single diameter, the measurement should be recorded as a continuous variable.

^bInduration/Swelling should be evaluated and graded using the functional scale as well as the actual measurement.

Vital Signs Assessment

Vital Signs ^a	Mild (Grade 1)	Moderate (Grade 2)	Severe (Grade 3)	Potentially Life Threatening (Grade 4)
Fever (°C) ^b	38.0 - 38.4	38.5 - 38.9	39.0 - 40	> 40
(°F) ^b	100.4 - 101.1	101.2 – 102.0	102.1 - 104	> 104
Tachycardia - beats per minute	101 – 115	116 – 130	> 130	Emergency room visit or hospitalization for arrhythmia
Bradycardia - beats per minute ^c	50 – 54	45 – 49	< 45	Emergency room visit or hospitalization for arrhythmia
Hypertension (systolic) - mmHg	141 – 150	151 – 155	> 155	Emergency room visit or hospitalization for malignant hypertension
Hypertension (diastolic) - mmHg	91 – 95	96 – 100	> 100	Emergency room visit or hospitalization for malignant hypertension
Hypotension (systolic) – mmHg	85 – 89	80 – 84	< 80	Emergency room visit or hospitalization for hypotensive shock
Respiratory Rate – breaths per minute	17 – 20	21 – 25	> 25	Intubation

^aSubject should be at rest for all vital sign measurements.

^bOral temperature; no recent hot or cold beverages or smoking.

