#### 6.5. Baseline

Unless otherwise specified, baseline is defined as the last non-missing measurement taken prior to reference start date (including unscheduled assessments). In absence of unscheduled assessments prior to dosing, the baseline will correspond to Day -1 assessment for physical examination, clinical safety laboratory, 12-lead ECG, PD, CCI measurements; and will correspond to Day 1, Predose assessment for vital signs. In the case where the last non-missing measurement and the reference start date coincide, that measurement will be considered pre-baseline if the assessment is planned per protocol to take place prior to study medication administration. Adverse Events (AEs) and medications commencing on the reference start date will be considered post-baseline unless otherwise indicated based on available start date/time combination or collected electronic Case Report Form (eCRF) data that identifies the

Visterra Insert
Customer Name/ Logo
Protocol VIS954-101
Page 20 of 42

Statistical Analysis Plan

individual event/medication as starting prior to study medication administration.

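### The upper systolic entry limit (160 mmHg) lies inside the protocol's own Severe range, which starts above 155 mmHg

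*Protocol*

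**What the plan says.** **Entry.** Protocol 5.2, exclusion 5: "Blood pressure > 160/100 mmHg or < 90/50 mmHg (may be repeated once if abnormal), at the screening visit or Day -1". Inclusion 10 (judged healthy) and exclusion 18 (judged inappropriate) add investigator discretion without a number.

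**Grading.** Protocol 8.3.2 sends the investigator to Section 10.5 to grade vital signs as adverse events. The rows there, in the order Grade 1, Grade 2, Grade 3, are:

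- "Hypertension (systolic) - mmHg 141 – 150 151 – 155 > 155"
- "Hypertension (diastolic) - mmHg 91 – 95 96 – 100 > 100"
- "Hypotension (systolic) – mmHg 85 – 89 80 – 84 < 80"

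**Stopping.** Protocol 7.1 stops the study and dose escalation on several triggers, one of which begins "Two participants experience a severe AE (Grade 3" and refers to the same scale. The serious-event trigger exempts clearly unrelated events. The Grade 3 trigger has no exemption for relatedness or for the baseline value.

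**Baseline.** Protocol 1.3, footnote f: "Vital signs measurements will be recorded on Day 1 within 30 minutes predose and at 2 and 4 hours postdose". SAP 6.5 says that, absent unscheduled assessments before dosing, baseline "will correspond to Day 1, Predose assessment for vital signs". This reading is separate from the two occasions that exclusion 5 covers.

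**Before dosing.** Protocol 8.4.1 says that occurrences between consent and dosing "will be recorded as Medical History / Current Medical Conditions, not as AEs".

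**The concern.** In a first-in-human study in healthy volunteers, the numeric entry limit should not admit someone whose reading already lies in the range that the same protocol calls Severe. For systolic pressure it does. The amendment summary describes the grading scale as suited to healthy participants, so the cut at 155 is the sponsor's own standard for this population. The protocol gives no reason for setting the entry limit 5 mmHg above it.

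Two things are at stake. The first is the entry standard itself. The second is the stopping count. A participant who enters at 156 to 160 and stays above 155 at predose has no Grade 1 or Grade 2 left for a hypertensive adverse event. A small rise, if judged clinically significant, counts as one of the two Grade 3 participants that stop the study. No information on the size of the change is lost, because Protocol 9.2.2.3 and SAP 18.4 summarize change from baseline.

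**Working it through.** The plan states no computed figure here, so the check compares thresholds. Criterion 5 is read in the usual way: either component out of range excludes. Values are whole mmHg.

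**Step 1. Grade every value that passes exclusion 5.**

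| Limit in criterion 5 | Eligible values | Ungraded | Grade 1 | Grade 2 | Grade 3 |
|---|---|---|---|---|---|
| Systolic, upper (hypertension row) | 90–160: 160 − 90 + 1 = 71 | 90–140: 51 | 141–150: 10 | 151–155: 5 | 156–160: 5 |
| Diastolic, upper (hypertension row) | 50–100: 100 − 50 + 1 = 51 | 50–90: 41 | 91–95: 5 | 96–100: 5 | none |
| Systolic, lower (hypotension row) | 90–160: 71 | 71 | none | none | none |

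The counts add up: 51 + 10 + 5 + 5 = 71 and 41 + 5 + 5 = 51. The fourth limit, diastolic below 50, has no row in Section 10.5. Of the three limits that can be compared, only the upper systolic limit overlaps Grade 3. The diastolic limit coincides with its Grade 3 cut, and the lower systolic limit stops just short of Grade 1 hypotension.

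**Step 2. Follow the reading to the stopping rule.** The reference for a post-dose change is the Day 1 predose value. The first Grade 3 value is 156, so the rise needed to reach it is 156 minus the predose value.

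| Day 1 predose systolic | Grades a later rise can reach | Rise to first Grade 3 value |
|---|---|---|
| 141–149 | 1, 2 or 3 | from 142, +14; from 149, +7 |
| 150–154 | 2 or 3 | from 150, +6; from 154, +2 |
| 155 | 3 | +1 |
| 156 or more | 3 | already in Grade 3 |

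Grade 4 applies in any row if the event leads to an emergency room visit or hospitalization for malignant hypertension. As an example, from a predose value of 142, a rise to 148 (+6) is Grade 1 and a rise to 153 (+11) is Grade 2. From 157, a rise to 163 (also +6) is Grade 3.

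**Step 3. Apply the limits on the consequence.** A reading of 156 to 160 before dosing is not an adverse event (Protocol 8.4.1). After dosing, an abnormal vital sign is an adverse event only if the investigator judges it clinically significant, and ordinary fluctuation of an existing condition without worsening does not count (Protocol 10.3.1). The route to a Grade 3 count therefore needs four things: entry at 156–160, a predose value still above 155, a further rise, and a judgement of clinical significance.

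**Step 4. Change the limit to 155.** Eligible systolic values become 90–155: 155 − 90 + 1 = 66, of which none is Grade 3.

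The documents do not give the number of entrants at 156–160, so no stopping probability is computed.

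**The case against.** The strongest reply is that entry limits and severity grades do different jobs. Section 10.5 grades adverse events, and nothing in the protocol ties eligibility to it. Other graded measures (pulse with Grade 3 below 45, respiratory rate with Grade 3 above 25, cholesterol with Grade 3 above 226) have no numeric entry limit and are left to the investigator. The match on diastolic pressure need not be deliberate, since diastolic 91–100 (Grades 1 and 2) is still eligible.

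Other safeguards narrow the group. Screening blood pressure is taken in triplicate. A participant must pass at both screening and Day -1. Exclusion 1 bars serious or unstable cardiovascular disease. Exclusion 8 bars most recent medication and makes no exception for antihypertensives.

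The fix is also imperfect. A predose value of 155 is one mmHg from Grade 3, and criterion 5 does not govern that reading. Finally, a clinically significant rise from an already high value is arguably something the stopping rule should count, and an error in that direction stops dosing and does not continue it.

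Much of this stands. It shows that the affected group is small, that the consequence is conditional, and that the change reduces the problem without removing it. The integer counts describe the scale and say nothing about how many participants are affected. What the reply does not do is stop a reading of 156–160 from passing. Where the protocol chose to set a number for blood pressure, that number admits values it calls Severe, and discretion under inclusion 10 or exclusion 18 does not explain why.

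**Conclusion.** The concern holds, at minor severity. Systolic 156–160 mmHg is eligible at screening and Day -1 and is Grade 3 on the protocol's own scale; the diastolic upper limit and the systolic lower limit have no Grade 3 overlap. The comparison rests on reading criterion 5 as excluding when either component is out of range. If both had to be exceeded, the systolic overlap would be wider and diastolic values above 100 could also pass.

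The effect on the stopping rule is conditional on the four events listed in the working, and it supplies only one of the two Grade 3 participants required. Few participants are likely to be affected.

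**What to change.** In Protocol 5.2, exclusion 5, replace 160 with 155 as the upper systolic limit. Leave the diastolic limits, the lower systolic limit, the single repeat and the two time points as they are. Sections 7.1 and 10.5 need no change.

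The cost is a one-line amendment, which needs IRB approval before use (Protocol 10.1.1), and perhaps a few more screen failures. The repeat already allowed lets a first reading of 156–160 be rechecked. No assessment is added.

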5.2.1 Meals and Dietary Restrictions

There are no meal or dietary restrictions.

5.2.2 Caffeine, Alcohol, and Tobacco

5.2.2.1 Caffeine

There are no restrictions on caffeine.

5.2.2.2 Alcohol

For the duration of the study, male participants should not consume more than 15 standard alcohol drinks per week (7 days) and female participants should not consume more than 10 standard alcohol drinks per week (7 days). A standard drink equals 10 g of alcohol.

Enrolled participants must abstain from consuming alcohol 48 hours prior to check-in to the study site on Day -1 through discharge.

5.2.2.3 Tobacco

Enrolled participants must abstain from consumption of nicotine containing products and cannabinoids while admitted to the study site (Day-1 through discharge).

5.2.2.4 Cannabinoids

Enrolled participants must abstain from consumption of cannabinoids from Day-1 through end of the study.

5.2.3 Activity

There are no restrictions on activity.

5.2.4 Other Restrictions

Blood donation (> 500 mL) is prohibited within 60 days prior to start of screening and/or donation of any plasma within 7 days prior to baseline (Day -1). Blood and plasma donation is also prohibited for the duration of the study and for 30 days after the last dose of study intervention.

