4.1 Overall Design

This is a phase 1, randomized, placebo-controlled, double-blind, single ascending dose, FIH study to assess the safety, tolerability, PK, and PD of VIS954 administered SC in healthy participants.

The study will be conducted in 6 sequential cohorts. Each cohort will enroll 9 participants, randomized to VIS954 or placebo at a ratio of 7:2 (7 VIS954:2 placebo). Each cohort will also optimally enroll 5 non-Japanese participants and 4 Japanese participants (achievement of this ratio is desired but not mandatory to advance to the next cohort). No more than one Japanese participant per cohort may be randomized to receive placebo.

The study is comprised of:

- A screening visit up to 28 days before dosing
- An in-house stay for 4 days, with admission to the study center on Day −1, SC administration on Day 1, and discharge on Day 3
- A postdose period with outpatient visits on Days 5 (± 2 days), 8 (+ 1 day),
 11 (± 1 day), 15, 22, 29, 36, 43, and 57 (for all visits not otherwise specified, ± 3 days)
- A final follow-up visit on Day 71 (± 3 days)

The total duration of the clinical study per participant will be up to 102 days (approximately 4 months), including the screening period.

Potential participants will be carefully screened for eligibility prior to study enrollment.

On Day 1, a single dose of VIS954 or placebo will be administered SC.

Sentinel participants will be utilized in each cohort; the first 2 non-Japanese participants in each cohort will be randomized to receive either VIS954 (n = 1) or placebo (n = 1) and will receive the study intervention at least 24 hours before the remaining 7 participants in the cohort are dosed. The safety data from each of the 2 sentinel participants will be reviewed over the 24-hour postadministration period to determine whether it is appropriate to proceed with dosing of the remaining participants in the cohort as planned. A similar review will occur for each dose escalation. The remaining 7 participants in a cohort will be randomized to receive VIS954 (n = 6) or placebo (n = 1).

Escalation to next dosing level will occur after review of blinded safety data when at least 7 participants have completed \geq 14 days in a cohort.

The planned dose of VIS954 for each cohort is summarized in Table 4.1-1.

Table 4.1-1 Study Intervention for Each Cohort						
Cohort	Study Intervention					
Cohort 1	VIS954 or placebo					
Cohort 2	VIS954 or placebo					
Cohort 3	VIS954 or placebo					

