5.1 Inclusion Criteria

Participants are eligible to be included in the study only if all of the following criteria apply:

- 1. Male or female participant between 18 to 55 years of age, inclusive, at the screening visit.
- 2. Non-Japanese participant: Participant does not meet the criteria specified below for 'Japanese Participant'.
- 3. Japanese participant: Participant is of Japanese descent as evidenced by verbal confirmation of familial heritage (a participant's 4 grandparents were born in Japan and recognized to be 'Japanese').
- 4. Body mass index between 18.0 and 30.0 kg/m², inclusive, at the screening visit.
- 5. Total body weight between 50.0 and 120.0 kg, inclusive, at the screening visit.
- 6. Capable of giving signed informed consent, which includes compliance with the requirements and restrictions listed in the informed consent form (ICF) and the protocol.
- 7. Willing and able to participate in the study for the defined duration of the study.
- 8. Female participants will be nonpregnant, nonlactating, and either postmenopausal for at least 1 year or surgically sterile for at least 3 months, or will agree to use highly effective methods of contraception from the period prior to study enrollment until 30 days after Day 56; women of childbearing potential must have a negative serum beta-human chorionic gonadotropin (β-hCG) test at screening and a negative urine pregnancy test at baseline prior to administration of the study intervention.

- 9. Male participants with female partners of childbearing potential must agree to use double barrier contraception or abstain from sex during the study and until 90 days after Day 56. Male participants must agree to refrain from sperm donation for the duration of the study and until 90 days after Day 56. This criterion may be waived for male participants who have had a vasectomy greater than 6 months prior to enrollment.
- 10. Healthy, as determined by prestudy medical evaluation (medical history, physical examination, vital signs, 12-lead ECG, and clinical laboratory evaluations), as judged by the principal investigator.

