7.3 Lost to Follow-up

A participant will be considered lost to follow-up if the participant repeatedly fails to return for scheduled visits and is unable to be contacted by the study site. The following actions must be taken if a participant fails to return to the clinic for a required study visit:

- The site must attempt to contact the participant and reschedule the missed visit as soon as possible, counsel the participant on the importance of maintaining the assigned visit schedule, and ascertain whether the participant wishes to and/or should continue in the study.
- Before a participant is deemed lost to follow-up, the investigator or designee must make every effort to regain contact with the participant (where possible, 3 telephone calls, and if necessary, a certified letter to the participant's last known mailing address or local equivalent methods). These contact attempts should be documented in the participant's medical record.
- Should the participant continue to be unreachable, the participant will be considered to have withdrawn from the study.

Discontinuation of the study as a whole are handled as part of Section 10.1.10.

8 Study Assessments and Procedures

Study procedures and their timing are summarized in the Schedule of Assessments (Table 1.3-1). Protocol waivers or exemptions are not allowed.

Adherence to the study design requirements, including those specified in the Schedule of Assessments, is essential and required for study conduct.

All screening evaluations must be completed and reviewed to confirm that potential participants meet all eligibility criteria. The investigator will maintain a screening log to record details of all participants screened and to confirm eligibility or record reasons for screening failure, as applicable.

Procedures conducted as part of the participant's routine clinical management (eg, blood count) and obtained before signing of the ICF may be utilized for screening or baseline purposes provided the procedures met the protocol-specified criteria and were performed within the timeframe defined in the Schedule of Assessments.

Laboratory results that could unblind the study will not be reported to investigative sites or other blinded personnel until the study has been unblinded.

The maximum amount of blood collected from each participant over the duration of the study, including any extra assessments that may be required, will not exceed 450 mL per month.

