10.4.2 Contraception Guidance

Contraception (described below) is required from the period prior to study enrollment, during the study, and until 30 days after the systemic exposure to the study intervention has ended for female participants (ie, 30 days after Day 56) and until 90 days after the systemic exposure to the study intervention has ended for male participants (ie, 90 days after Day 56).

CONTRACEPTIVES^a ALLOWED DURING THE STUDY INCLUDE:

Highly Effective Methods^b That Have Low User Dependency

- Implantable progestogen-only hormone contraception associated with inhibition of ovulation^c
- Intrauterine device
- Intrauterine hormone-releasing system^c
- Bilateral tubal occlusion
- Azoospermic partner (vasectomized or due to a medical cause)
 Azoospermia is a highly effective contraceptive method provided that the partner is the sole sexual partner of the participant of childbearing potential and the absence of sperm has been confirmed. If not, an additional highly effective method of contraception should be used. Spermatogenesis cycle is approximately 90 days.
 Note: Documentation of azoospermia for a male participant can come from the site personnel's review of the participant's medical records, medical examination, or medical history interview.

Highly Effective Methods^b That Are User Dependent

Combined (estrogen- and progestogen-containing) hormonal contraception associated with inhibition of ovulation^c

- Oral
- Intravaginal
- Transdermal

Progestogen-only hormone contraception associated with inhibition of ovulation³

- Oral
- Injectable

Sexual abstinence

Sexual abstinence is considered a highly effective method only if defined as refraining from heterosexual intercourse during the entire period of risk associated with the study intervention. The reliability of sexual abstinence needs to be evaluated in relation to the duration of the study and the preferred and usual lifestyle of the participant.

- a) Contraceptive use by men or women should be consistent with local regulations regarding the use of contraceptive methods for those participating in clinical studies.
- b) Failure rate of < 1% per year when used consistently and correctly. Typical use failure rates differ from those when used consistently and correctly.
- c) Male condoms must be used in addition to hormonal contraception.

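### For a participant who withdraws early, the blood and plasma donation ban can lapse up to 25 days before the protocol's own end of systemic exposure (Day 56)

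*Protocol*

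**What the plan says.** Protocol Section 5.2.4 restricts donation after enrolment with two limbs: "Blood and plasma donation is also prohibited for the duration of the study and for 30 days after the last dose of study intervention". Section 6.1 provides for a single subcutaneous dose on Day 1, so the first dose is also the last.

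Section 10.4.2 gives the protocol's end of systemic exposure and counts contraception from it: "until 30 days after the systemic exposure to the study intervention has ended for female participants (ie, 30 days after Day 56"). Men follow the same anchor with 90 days. Inclusion criterion 9 applies it to sperm donation: "Male participants must agree to refrain from sperm donation for the duration of the study and until 90 days after Day 56". Section 8.4.5 also counts pregnancy follow-up from Day 56.

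Section 5.2.4 does not say whose study duration is meant. Section 4.4 defines the end of the study at trial level, as the last participant's last visit. Section 4.1 gives a figure for each person: "The total duration of the clinical study per participant will be up to 102 days (approximately 4 months), including the screening period". Section 7.2 allows withdrawal at any time, and nothing in either document extends the donation ban for someone who has withdrawn.

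**The concern.** The post-dose limb of the donation ban is shorter than the exposure period the protocol states elsewhere. For a completer this is harmless, because the study-duration limb outlasts both. For someone who leaves early, the study-duration limb may stop at withdrawal, leaving only the 30 days after dosing. That person would then be free to give blood or plasma while the protocol still treats them as systemically exposed to a first-in-human antibody.

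Donation of blood and plasma is also the exception among the post-exposure precautions. Contraception, sperm donation and pregnancy follow-up all run from Day 56. The sperm-donation rule has the same two-limb form but covers early leavers on either reading, because its second limb is tied to Day 56 and not to the dose.

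**Working it through.** **Inputs**

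- Dosing: once, on Day 1 (Protocol 6.1). The SAP (6.4) numbers the day of dosing as Day 1.
- Post-dose limb: 30 days after the last dose (Protocol 5.2.4).
- End of systemic exposure: Day 56 (Protocol 10.4.2).
- Final visit: Day 71 ± 3 days, so Day 68 to 74; screening up to 28 days before dosing (Protocol 4.1).
- VIS954 recipients: 6 cohorts × 7 = 42 (Protocol 4.1).

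**The plan's own figure.** Per-participant duration = 28 + 71 + 3 = 102 days. This reproduces the figure in Section 4.1 and confirms that the protocol uses study duration in a per-person sense there.

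**Per-participant reading.** The post-dose limb ends on Day 1 + 30 = Day 31. For withdrawal on Day d, the ban ends on max(d, 31) and the gap is max(0, 56 − max(d, 31)).

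| Withdrawal day | Ban ends | Gap to Day 56 |
|---|---|---|
| Day 31 or earlier | Day 31 | 25 days |
| Day 36 | Day 36 | 20 days |
| Day 43 | Day 43 | 13 days |
| Day 56 or later | withdrawal day | 0 days |
| Completer | Day 68–74 | 0 days |

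If Day 56 meant 56 elapsed days after dosing, the maximum would be 26 days.

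**Trial-level reading.** The ban would run to the last participant's last visit, so the gap is normally 0. With six cohorts there are 5 escalation steps of at least 14 days, or at least 70 days in all. A Cohort 1 participant among the first seven dosed would be barred to at least Day 68 + 70 = Day 138, if all six cohorts run and someone in Cohort 6 completes. Individual participation ends by Day 74. The 30-day limb would matter only if the last participants all left early, since for the last person dosed Day 31 precedes Day 68–74.

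**Which reading fits the text.** The same phrase governs individual obligations elsewhere:

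- Inclusion criterion 7: "Willing and able to participate in the study for the defined duration of the study".
- Exclusion criterion 12: "For the duration of the study, enrolled male participants should not consume more than 15 standard drinks per week (7 days"). Section 5.2.2.2 repeats the rule.
- Section 8, on the monthly blood-volume limit: "The maximum amount of blood collected from each participant over the duration of the study".

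These uses, with the per-person duration in Section 4.1, favour individual participation, but they do not exclude the trial-level meaning.

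**Number of people.** The protocol gives no withdrawal rate. At an assumed 2–10%, 42 × 0.02 = 0.84 to 42 × 0.10 = 4.2 VIS954 recipients would withdraw. Treating every withdrawal as falling before Day 56 makes this a ceiling on those free to donate in the window. If an assumed 1–10% of them donated, the expected number of donors would be 0.84 × 0.01 = 0.008 to 4.2 × 0.10 = 0.42.

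**The case against.** The gap depends on an undefined phrase, and the only formal definition of the end of the study (Section 4.4) is the one that closes it. A ban to Day 138 for Cohort 1 is not absurd either: men's sperm-donation restriction already runs to 56 + 90 = Day 146. The redundancy argument is weak too, because on the per-participant reading the 30-day limb binds only people who leave before Day 31. All of this stands, and it is why the finding is conditional. The individual reading rests mainly on how the phrase is used elsewhere.

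The second objection is about purpose. The preceding sentence of Section 5.2.4 limits donation before screening and baseline, which cannot concern drug exposure, and Section 8 caps study blood draws at 450 mL per month. The rule may therefore protect the participant's own blood volume, in which case it has no need to follow Day 56. This stands in part. However, the second limb is counted from the last dose and not from the last blood sample, which suggests that exposure is at least part of the purpose.

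Third, dose levels are redacted, so exposure between Day 31 and Day 56 cannot be checked by cohort, and the consent form, which is not available, may already give a donation end date. Both limits stand. Day 56 is nevertheless the only end of exposure the protocol states, and the sponsor relies on it for its other precautions.

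Finally, one could simply ask the sponsor to define the phrase. That would settle the ambiguity, but if the answer is individual participation, the gap remains.

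**Conclusion.** The concern holds as a minor, conditional safety point. If study duration means individual participation, the ban can end up to 25 days before the stated end of exposure for anyone who withdraws before Day 56. For completers the gap is zero, and on the trial-level reading it is normally zero.

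The conclusion takes Day 56 as the end of exposure for every cohort and assumes the ban is at least partly about exposure; the documents confirm neither the exposure by cohort nor the purpose. The head counts rest on assumed withdrawal and donation rates, and the expected number of actual donors is below one throughout the assumed range. The documents quantify no risk to donors or recipients. Confidence is medium, because the phrase is ambiguous.

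**What to change.** In Protocol Section 5.2.4, keep the study-duration limb and replace the limb counted from the last dose with: *and at least through Day 56, including for participants who withdraw early*. This removes the gap on both readings and gives site staff a fixed minimum date to tell a departing participant.

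The cost is one sentence, plus matching consent wording if the consent form repeats the rule. Early leavers, including those on placebo, would be restricted for up to 25 days longer; completers would see no change. Visits, sample size and analysis are unaffected. Any margin beyond Day 56 is for the sponsor to decide and is not needed to close this gap.
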